11.2.6 Cost and Cost Effectiveness

Health resources utilised between study groups will be identified, measured, and valued to obtain the total costs of each intervention. Length of stay and subsequent hospital admissions up to 12 months post-surgery will be valued (national hospital pricing model) and prices adjusted based on 3% annual inflation. The use of all health services (including adjuvant treatments) within 12 months of surgery will be collected and valued at each site in \$AUD. Cost of AEs will be allocated depending on their severity as determined using the CTCAE V5.0. To assess the value of health outcomes for each surgical option, the EQ-5D-5L will be used to estimate utility scores and calculate gains in quality adjusted life years (QALYs) associated with the intervention.

A Markov model will simulate how patients progress through health states and incur costs and QALYs. Model input parameters (e.g., transition probabilities, costs, and utility scores) will be obtained from this trial and other relevant published literature. The incremental costs and QALYs will be compared to calculate the incremental cost effectiveness ratio (ICER). A willingness to pay threshold of \$50,000/QALY, a commonly used threshold in the literature, will be used as a decision rule [46]. Probabilistic sensitivity analysis will be conducted to characterise the uncertainty in the results of the economic evaluation. Value of implementation analysis will be conducted to estimate the expected net health and monetary benefits gained with the adoption of groin node ultrasound surveillance.

11.2.9 Disease-Free and Overall Survival (DFS, OS)

Participants will be followed for 12 months and assessed for local, regional, or distant recurrence. Participants will be seen every 3 to 6 months. Clinical assessments will be performed at each visit. Clinical assessment, radiological work-up ± histological confirmation of recurrence will prove the presence of recurrent disease.

DFS is defined as time until the first recurrence or death from any cause. In patients without recurrence, or lost to follow-up, DFS will be censored on the date of the last follow-up visit. DFS will be compared between treatment arms using methods for the analysis of censored data. Variables to be evaluated for effect on DFS will include clinical management group (groin LND, ultrasound groin surveillance), age, medical comorbidities.

12 Trial Monitoring and Oversight

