| | 
 If the groin ultrasound is negative/normal (n=180), participants will be randomised 2:1 to receive either a groin LND (n=60) or bilateral groin USM every 2 months along with clinical examination every 3 months for a period of 12 months (n=120; no upfront groin LND). 
All participants will receive appropriate surgical excision of the primary tumour (radical wide local excision or radical vulvectomy). All lymph nodes will undergo central pathology review [1]. Postoperative treatment will follow local institutional treatment guidelines.
 |
| 
Stage details and number of participants
 | 
240 participants in total:
 
 Ultrasound negative/normal groin nodes (120 undergoing groin USM every 2 months along with clinical examination every 3 months and 60 upfront groin IFL/SNB) Ultrasound suspicious/indeterminate groin nodes (60 having upfront groin IFL/SNB) |
| 
Study Duration
 | 
Enrolment for this study is projected to conclude within a 4-year timeframe. The study will be deemed complete once 180 participants have been enrolled, randomised, and successfully completed a 12-month follow-up period.
 |

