5.6 Secondary Endpoint

1. HRQL and PROMS as measured by the EQ-5D and FACT-V at baseline, 8 weeks, 6 months, and 12 months
2. Morbidity at 12 months after surgery
3. Lower limb lymphoedema: incidence up to 12 months after surgery
4. Cost and cost effectiveness at 12 months post-surgery
5. Clinical accuracy of high-resolution ultrasound to predict groin lymph node involvement
6. Disease-free survival (DFS) and overall survival (OS)
7. Utility of biomarkers to reliably reflect the presence or absence of positive groin lymph nodes
8. Explore novel biomarkers for vulvar cancer

6. Study Design

A phase II, open label, multicentre, three-group, randomised clinical trial (ANVU).

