6.3 Exclusion Criteria

- Women with non-invasive vulvar conditions (e.g. non-invasive non-mammary Paget's disease)
- SCC of the vulvar with depth of invasion \leq 1 mm
- Clinical or medical imaging evidence of regional and/or distant metastatic disease
- Serious concomitant systemic disorders incompatible with the study (at the discretion of the investigator)
- Other prior malignancies $<$ 5 years before inclusion, except for successfully treated keratinocyte skin cancers, or ductal carcinoma in situ
- Estimated life expectancy of \leq 6 months

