11.1 Sample Size & Stopping Rules

Incurable groin recurrence has a >90% mortality within 12 months [21]. We estimate the probability of incurable groin recurrence within 12-month of an upfront LND, i.e., $P(\text{recur}|\text{LND})$, to plausibly be up to 3% in usual practice. This is based on a 32% prevalence of positive nodes in clinical stage I/II vulva cancer [41] and that the false negative rate for routinely used SNB is up to 8.8% [7,42]. A

recurrence probability given groin USM, i.e., $P(\text{recur}|\text{USM})$, of 6% would be acceptable to avoid the side-effects of LND based on our decision analysis using best available evidence, expert judgement, and consumer input. $P(\text{recur}|\text{USM})$ will be characterised using a Bayesian Beta-Binomial model with priors informed by our pilot study (1/32 recurrences) [10]. We will declare groin USM acceptably safe if the probability that $P(\text{recur}|\text{USM}) < 0.06$ is 80%. A Bayesian Monitoring approach will ensure participant safety (MD Anderson Biostatistics BTOX routine www.trialdesign.org/#software). Stopping early due to unacceptably safety will be triggered if there is more than a 70% probability that $P(\text{recur}|\text{USM})$ exceeds 0.06 (i.e., recurrence rate of at least 5/40, 6/60, 7/80, 9/100, or 10/120). We anticipate that $P(\text{recur}|\text{USM})$ is truly 3% and thus calculate that ANVU has less than a 2% probability of incorrectly stopping early for unacceptable safety and a 0.85 probability of correctly declaring acceptable safety at N=120. The statistical design accommodates expansion beyond N=120 USM participants (e.g., as a protocol amendment) if neither safety criterion is reached and the predicted probability of success given expansion is at least 80%.

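### Section 11.2.9 counts death from any cause as a DFS event, then censors every patient without recurrence: the two sentences contradict each other

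*Protocol*

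**What the plan says.** DFS and overall survival (OS) are listed together as secondary endpoints in the Synopsis and in section 5.6. The working definition appears only in section 11.2.9:

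- Event: "DFS is defined as time until the first recurrence or death from any cause".
- Censoring, in the sentence that follows: "In patients without recurrence, or lost to follow-up, DFS will be censored on the date of the last follow-up visit".
- Comparison: "DFS will be compared between treatment arms using methods for the analysis of censored data".
- Follow-up: "Participants will be followed for 12 months and assessed for local, regional, or distant recurrence".

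The censoring sentence does not limit itself to patients who are alive and has no exception for death. Section 11.2.9 also says that age and medical comorbidities will be examined for their effect on DFS. No method is named for handling death separately, for example as a competing risk.

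**The concern.** A protocol may leave censoring detail to the statistical analysis plan. This one states a censoring rule, and the rule conflicts with its own event definition. Whoever programs the endpoint has to override one of the two sentences.

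If the censoring sentence prevails, deaths without recurrence leave the event count and DFS looks better than it is. Such deaths are plausible within 12 months. Section 6.3 excludes only women with a life expectancy of 6 months or less, and section 6.4 has a randomisation stratum for a Charlson index of 5 or more. Age and comorbidity, the covariates named for DFS, would be expected to act largely through these deaths. The trial aims to de-escalate surgery without harming survival, so an inflated DFS would be an unhelpful summary to report beside that aim.

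**Working it through.** **1. The two sentences applied to three cases**

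| Case | Under the definition | Under the censoring sentence |
|---|---|---|
| Alive, no recurrence at month 12 | No event; censored | Censored at last visit |
| Recurrence at month 4 | Event at month 4 | Event at month 4 |
| Dies at month 5 with no recurrence; last visit month 4 | Event at month 5 | Censored at month 4 |

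Only the third case differs, and it differs for every death without recurrence.

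**2. Plan figures to reproduce**

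There are none. The protocol gives no DFS event count, rate or power, and the figures in section 11.1 do not use this rule.

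**3. Size of the effect, on assumed rates**

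Inputs:

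- N = 180 randomised (Synopsis: "If the groin ultrasound is negative/normal (n=180), participants will be randomised 2:1").
- r = 12-month risk of any recurrence. Not given. Assumed 6% and 15%. The 6% borrows the figure that section 11.1 treats as acceptable for groin recurrence under ultrasound monitoring, which is narrower than recurrence at any site.
- d = 12-month risk of death without recurrence. Not given. Assumed 1%, 3% and 5%.
- The two event times are taken as independent and exponential. The short gap between last visit and death is ignored.

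Formulas:

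- 12-month DFS as defined = (1 − r)(1 − d)
- 12-month estimate under the literal rule = 1 − r
- Overstatement = (1 − r) − (1 − r)(1 − d) = (1 − r)d
- Events as defined = N[1 − (1 − r)(1 − d)]
- Share of events lost = h_d / (h_r + h_d), where h_r = −ln(1 − r) and h_d = −ln(1 − d)

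Worked case, r = 6% and d = 3%:

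- DFS as defined = 0.94 × 0.97 = 0.912; literal rule 0.940; overstatement 0.94 × 0.03 = 2.8 points.
- Events as defined = 180 × (1 − 0.9118) = 15.9.
- Share lost = 0.0305 / (0.0619 + 0.0305) = 33%, or about 5.2 deaths, leaving 10.6 events.

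| r | d | DFS as defined | Literal rule | Overstatement (points) | Events: defined / literal | Share lost |
|---|---|---|---|---|---|---|
| 6% | 1% | 93.1% | 94.0% | 0.9 | 12.5 / 10.7 | 14% |
| 6% | 3% | 91.2% | 94.0% | 2.8 | 15.9 / 10.6 | 33% |
| 6% | 5% | 89.3% | 94.0% | 4.7 | 19.3 / 10.5 | 45% |
| 15% | 1% | 84.1% | 85.0% | 0.9 | 28.5 / 26.9 | 6% |
| 15% | 3% | 82.5% | 85.0% | 2.6 | 31.6 / 26.6 | 16% |
| 15% | 5% | 80.7% | 85.0% | 4.3 | 34.6 / 26.3 | 24% |

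The overstatement stays close to d. The share of events lost depends heavily on the assumed r.

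**4. The contrast between arms**

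The difference in 12-month DFS (monitoring minus dissection) shifts by (1 − r_U)d_U − (1 − r_L)d_L, where U is ultrasound monitoring and L is dissection. For illustration, take r_U = 6%, r_L = 3% (section 11.1 puts incurable groin recurrence after dissection "to plausibly be up to 3% in usual practice") and d = 3% in both arms. The shift is 0.94 × 0.03 − 0.97 × 0.03 = 0.0282 − 0.0291 = −0.09 points, which is negligible. It becomes material only if d differs by arm, and the protocol gives no basis for saying that it does or in which direction.

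**The case against.** The strongest reply is that the definition governs. Censoring ordinarily applies only to patients who have not had the event, so a careful analyst would count the deaths and read the next sentence as loose drafting for without recurrence or death. That is probably the intent. Section 11.2 also promises an analysis plan in the estimand framework, where the wording could be put right. This makes a miscoded analysis less likely, but it does not remove the contradiction.

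Four stronger readings are tempting, and the document does not support them:

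- *The plan has decided never to count deaths without recurrence.* The adjacent definition counts them. This is a contradiction, not a settled choice.
- *A woman who recurs and is later lost to follow-up is also censored.* This reading is strained. Her time to first recurrence is already fixed, and loss to follow-up naturally means loss before an event.
- *The comparison between arms is biased.* Surgical morbidity after dissection and undetected disease under monitoring would push in opposite directions, and randomisation is stratified by Charlson index. Neither the size nor the sign of any bias can be determined.
- *More than a third of DFS events would be lost.* With r = 10% and d = 6%, 180 × (1 − 0.90 × 0.94) = 27.7 defined events fall to about 17.4, a loss of 37%. That pairs low recurrence with high death, both assumed, so it is not a headline figure.

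The consequences are also limited. DFS is a secondary endpoint with no threshold or decision rule, and deaths still enter the evidence through OS.

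**Conclusion.** Wrong as written. The event definition and the censoring rule in section 11.2.9 cannot both be followed for a woman who dies without recurrence, and no other section settles which applies. If the censoring sentence is applied, the reported quantity is time to recurrence with deaths censored. Twelve-month DFS is then overstated by about 1 to 5 percentage points for an assumed 1% to 5% risk of death without recurrence. That range rests on the assumed rates and on independence of the two event times. The contradiction itself rests on neither. The primary endpoint, OS, the sample size and the stopping rules do not depend on this rule.

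**What to change.** Replace the censoring sentence in section 11.2.9 with wording such as:

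> Patients alive without recurrence, including those lost to follow-up before any event, are censored at their last follow-up visit. Death without prior recurrence is a DFS event on the date of death.

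Carry the same rule into the statistical analysis plan. The cost is one sentence, and no new data are needed, because OS already requires dates of death to month 12. SAE collection stops at 6 months (sections 10.2 to 10.4), so the sponsor should confirm that later deaths are captured with their dates by another route, such as the disease-status or adverse-event forms. Reported DFS may come out slightly lower than under the literal rule.

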12.1 Patient Safety

The number of enlarged, palpable groin node metastases/recurrences in all three groups will be monitored continuously and trial stopping rules are in place if these numbers exceed the upper limit of normal. Ultrasound is non-invasive and does not use radiation. In Australia, all ultrasound scans will be performed by registered sonographers with a postgraduate degree recognised by the Australian Sonographers Accreditation Registry (ASAR) and monitored by the TMC. At International sites, all ultrasound scans will be performed by sonographers with equivalent credentials. Blood tests will be performed up to 30 days prior to surgery (as part of routine blood tests), 8 weeks post-operation and then every 2 months for ultrasound patients. The risk of participants in having the intervention is to develop a clinically apparent groin node recurrence that would grow to a large size undetected and that would lead to poor survival outcomes (potentially leading to death). To mitigate this risk, we have implemented precautionary measures. Following surgery to remove the primary vulvar tumour, participants in the intervention group will have a groin ultrasound scan every 2 months and a clinical examination every 3 months, for a period of 12 months. Eligibility for participation in this study requires a commitment from patients to adhere to these frequent follow-up intervals and only participants with a normal/negative baseline groin node ultrasound are eligible to be randomised.

The prospective study's design, stringent inclusion and exclusion criteria, a well-defined follow-up schedule involving bi-monthly ultrasounds and clinical examinations every three months, use of a synoptic reporting format for groin ultrasound findings and the appropriate allocation of resources, including dedicated study staff, along with the comprehensive training of sonographers will effectively reduce the likelihood of participants experiencing unfavourable outcomes. However, it's important to mention that even when patients undergo groin node dissection (LND) as part of their standard treatment, the risk of subsequent groin node metastasis and the associated risk of death fall within the range of 3% to 10%, as indicated in published literature [6].

12.2 Quality Assurance

A central histopathology review will categorise involved nodes into positive, micro-metastasis, or isolated tumour cells.

12.3 Trial Management Committee (TMC)

The role of the TMC is to provide overall supervision of the trial. The TMC will include the CI, clinicians, and experts from relevant specialties and ANVU trial staff from QCGC Research. The TMC will be responsible for overseeing the trial and ensuring that the trial is conducted to the required standards. The group will meet approximately two to three times a year (more if required) and will provide updates to PIs via newsletters and/or at Investigator meetings.

Following each meeting, the TMC will recommend that the study continues according to the protocol or may suggest changes to the protocol based on the outcome of the data review. The TMC will review substantial amendments to the protocol prior to submission to the HREC. All PIs will be kept informed of substantial amendments through their nominated responsible individuals.

The TMC will also review the recommendations of the Independent Data Safety Monitoring Committee (IDSMC) and, on consideration of this information, recommend any appropriate amendments/actions for the trial as necessary.

12.4 Independent Data Safety Monitoring Committee (IDSMC)

The trial executive will monitor the incurable groin recurrence within 12-months according to the schedule presented in [Section 11.1](#).

The IDSMC will provide independent advice on enrolment, patient safety, data completeness and efficacy, scientific validity, and data integrity, as well as critical efficacy endpoints. The members of the IDSMC are not nor have ever been participants in the ANVU Trial.

The first safety analysis will be reviewed at 6 months or after 20 participants have completed surgical treatment (whichever comes first). The IDSMC will then meet approximately once or twice a year, or more often if required.

Following each meeting, the committee will provide a written report to the TMC and recommend continuation of the trial or protocol changes based on the outcome of the data review. The IDSMC is advisory to the TMC and in exceptional cases can recommend premature closure of the trial to the TMC due to safety reasons.

The IDSMC membership includes the following:

- Two independent gynaecological oncologists who are otherwise not involved with the trial.
- At least one independent statistician who is otherwise not involved with the trial.
- At least two specialists from a profession related to gynaecological oncology (pathology, medical imaging, medical oncology, radiation oncology, etc.) who is otherwise not involved with the trial.
- Additional members may be co-opted as necessary.

All IDSMC members will be required to agree to an IDSMC Terms of Reference.

12.5 Recurrence Adjudication Committee (RAC)

The objective of adjudication is that a well-recognised group of experts in the field of Gynaecological Oncology provide their input based on their best judgement and expertise in vulvar cancer, the location of the recurrence, and the date of this recurrence in participants accrued to the ANVU trial. The members of the RAC are not nor have ever been participants in the ANVU Trial. Their review will provide an independent, unbiased, clinical review of documented recurrences and this will be blinded to randomised treatment. The RAC review will be scheduled every 6 months from year 2 onwards for the duration of the study. A summary of each recurrence, including all correlating source documents (and translation forms if applicable), will be provided for the clinical review.

Adjudication ensures accuracy due to the high level of expertise of members, independency to avoid any bias, and consistency by using a centralised committee.

The RAC is responsible for reviewing each reported recurrence. Their work is independent and impartial. This type of review is to ensure accuracy and consistency of events reported in this study.

All RAC members will be required to read and agree to the RAC Terms of Reference.

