| Study Objectives | 
Primary objective:
 
 To determine the incidence of palpable, fixed to skin and histologically positive groin nodes at 12 months in women with vulvar cancer randomised to serial high-resolution groin USM versus standard surgical groin LND 
Secondary objectives:
 
 Compare Patient Reported Outcomes (PROMS) and Health-Related Quality of Life (HRQL) between the groups Compare pain and adverse events (morbidity) between the groups Compare lower limb lymphoedema between the groups Compare cost and cost effectiveness between the groups Determine the diagnostic accuracy of pre-operative, standardised high-resolution groin ultrasound to identify groin node metastasis. 
Translational research objective:
 
 To assess the role of blood and tissue molecular biomarkers to accurately determine the burden of disease (positive lymph nodes) in vulvar cancer, assist with risk stratification and aid disease surveillance |
| Study Endpoints | 
Primary endpoint:
 
 Incidence of clinically palpable, fixed to skin and histologically positive groin lymph nodes (node metastasis) at 12 months after surgical excision of the primary vulvar tumour |

| | |

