Our pilot data confirm that groin ultrasound is a clinically feasible alternative to LND [17]. Cls [name] and [name] undertook a pilot study to determine whether 3-monthly groin USM could be performed in lieu of upfront groin LND after a negative bilateral groin ultrasound in 32 women with apparent Stage 1 or 2 vulvar cancer. Three positive nodes (9.4%) were detected during a median

follow-up of 37 months (none lost to follow-up) and 29 patients could be spared a groin LND. All ultrasound-detected positive nodes developed within 12 months. One participant died of her groin recurrence (3.1%). The sensitivity of serial groin USM was 100% (95% CI: 44-100%), with specificity of 97% (95% CI: 83-99%) and negative predictive value of 100% (95% CI: 88-100%). These compelling pilot data justify a larger study on serial groin ultrasound in lieu of upfront groin LND in selected patients with vulvar cancer. In this study sensitivity of the monitoring via 2-monthly ultrasonography was calculated as the proportion of true-positive ultrasonic scans (confirmed histologically) of the total number of true-positive and false-negative scans. Similarly, the specificity was calculated as the proportion of true-negative scans of the total number of true-negative and false-positive scans. A false-positive scan was determined after fine needle cytology was negative; two nodes were surgically removed and found to be negative histologically.

Standardisation of groin ultrasound is achievable. Encouraged by our pilot study, CIA [name] recently completed a prospective feasibility study of synoptic reporting of groin ultrasound findings in women with vulvar cancer (pre-ANVU study, ACTRN12622000886785; publication in preparation). It applied 10 rigorous criteria for groin node ultrasound. Eligible women underwent groin ultrasound prior to planned groin LND. All 20 women had all 10 criteria reported. This successful feasibility and quality assurance study warrants using those 10 criteria in our ANVU trial. Furthermore, the pre-ANVU study attracted the award of the Australian Society of Gynaecological Oncologists Tony McCartney Surgical Innovation prize in 2023, citing the work represents the “perfect synthesis of reducing significant morbidity associated with vulvar cancer surgery ... that enables de-escalation of vulvar cancer surgery [that is] safe for patients”.

4. Expected Outcomes and Health Impact

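### The adjudication committee is not asked whether a groin node was palpable and skin-fixed, and Sections 11.1 and 11.2.1 do not say that its classification is the one analysed

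*Protocol*

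**What the plan says.** Section 12.5 sets out what the RAC does. Its members are to "provide their input based on their best judgement and expertise in vulvar cancer, the location of the recurrence, and the date of this recurrence". The cases are those that sites have declared: "The RAC is responsible for reviewing each reported recurrence". The review is a "clinical review of documented recurrences and this will be blinded to randomised treatment", and the material is generous: "A summary of each recurrence, including all correlating source documents (and translation forms if applicable), will be provided for the clinical review". Further rules exist but are not shown: "All RAC members will be required to read and agree to the RAC Terms of Reference".

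The synopsis defines the primary endpoint as "Incidence of clinically palpable, fixed to skin and histologically positive groin lymph nodes (node metastasis) at 12 months". The body words it differently:

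- Section 5.5 names enlargement and palpability, but not skin fixation or histology.
- Section 11.1 counts incurable recurrence in the groin.
- Section 11.2.1 estimates the proportion with enlarged palpable nodal metastases, timed from randomisation rather than from surgery.

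Neither 11.1 nor 11.2.1 mentions the RAC. Section 12.4 has the trial executive monitor the count.

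The trial is open label (Section 6). In the USM arm the groin is examined at the site or by a local gynaecologist (Section 7.5.2), and action on a suspicious scan follows the clinician's judgement (Section 6.5.3). Histology is reviewed centrally (Section 12.2).

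**The concern.** In the USM arm a small node found by scan and then removed is the strategy working, while a palpable, skin-fixed, positive node is the failure that the trial counts. Both are histologically positive, so central pathology cannot tell them apart. Palpability and fixation can, and these are clinical findings recorded by people who know the arm. Section 12.5 does not put that question to the RAC and does not expressly send it nodes found by scan.

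The pilot shows that the call is a real one. Section 3.4 reports: "Three positive nodes (9.4%) were detected during a median" follow-up of 37 months among 32 women, with one death from groin recurrence. Section 11.1 then carries 1/32 forward as the recurrence figure. Three positive nodes became one event, and the protocol gives no rule for doing so. Unblinded classification that lowered the USM count would move the result towards a declaration of safety, for an event that Section 11.1 says kills more than 90% within 12 months.

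**Working it through.** **Inputs from Section 11.1.** Declare safety if the posterior probability that the USM rate is below 0.06 is 80%. Stop if the probability that it exceeds 0.06 is above 70%, printed as 5/40, 6/60, 7/80, 9/100 and 10/120. At a true 3%, the stated chance of declaring safety is 0.85 and the stated chance of wrongly stopping is under 2%.

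**Assumption: the prior.** The protocol says only that it is informed by 1/32. Two readings were used: Beta(0.5 + 1, 0.5 + 31) = Beta(1.5, 31.5), and half weight on the pilot, Beta(0.5, 15.5). With x events in n women the posterior is Beta(a + x, b + n − x).

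**Reproducing the plan's figures with Beta(1.5, 31.5).**

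| n | Printed limit | Pr(rate > 0.06) at limit | One event fewer |
|---|---|---|---|
| 40 | 5 | 0.805 | 0.656 |
| 60 | 6 | 0.754 | 0.607 |
| 80 | 7 | 0.710 | 0.567 |
| 100 | 9 | 0.784 | 0.670 |
| 120 | 10 | 0.749 | 0.635 |

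All five limits are returned, and Beta(0.5, 15.5) returns them too. At n = 120, Pr(rate < 0.06) is 0.859 with 5 events, 0.758 with 6 and 0.632 with 7 (0.874, 0.770 and 0.638 under the second prior). So the outcomes are: safe at 5 or fewer, neither criterion at 6 to 9, and the stopping limit at 10. At a true 3%, P(X ≤ 5) for Binomial(120, 0.03) is 0.847, essentially unchanged by the interim stops, against the stated 0.85. The chance of stopping is 0.017 before 120 and 0.018 including it. Beta(1, 31) gives a safety limit of 6 but does not return the printed stopping limits.

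**How many nodes need the call.** If the pilot proportion carries over, 120 × 3/32 = 11.25, or about 11 USM women with a positive node, against a safety limit of 5 events.

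**How often the count sits at the edge.** Chance of reaching 120 under the stopping limits with the count shown:

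| True rate | Exactly 6 | 6 or 7 |
|---|---|---|
| 3% | 8% | 12% |
| 5% | 16% | 29% |
| 6% | 14% | 28% |

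**Effect of a fixed number of reclassified events, at the final count only.** At a true 6% the chance of declaring safety is 0.267. It becomes 0.411 if one failure is recorded as an early find (true count up to 6 passes) and 0.548 if two are (up to 7).

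**Effect of a misfiling proportion q.** The recorded rate is p(1 − q), applied at every look. The values of q are illustrative; the documents give none.

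| True rate p | q | p(1 − q) | P(declare safe) |
|---|---|---|---|
| 6% | 0 | 0.060 | 0.267 |
| 6% | 10% | 0.054 | 0.365 |
| 6% | 20% | 0.048 | 0.481 |
| 6% | 30% | 0.042 | 0.608 |
| 8% | 0 | 0.080 | 0.075 |
| 8% | 10% | 0.072 | 0.130 |
| 8% | 20% | 0.064 | 0.213 |

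**The case against.** Section 12.5 asks for expert judgement as well as place and date, supplies all source documents, and aims at accurate and consistent events. The Terms of Reference, or a statistical analysis plan, may define the cases and say whose classification is analysed. This stands as a limit: that the RAC is confined to location and date is the natural reading of a loosely built sentence, not an express restriction. It does not remove the point. The protocol itself sets the remit and the case selection, and sets them too narrowly for its primary endpoint.

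A reader might infer that local clinicians decide the endpoint. No section says so; it follows only from nobody else being assigned. Central pathology, uploaded scan reports and USM visit reports leave a dated record.

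A reader might also infer that scan-detected nodes never reach the RAC. That is not established. Section 7.5 assesses all participants for regional recurrence, disease status is recorded at follow-up, and the recurrence description in Section 11.2.9 could cover a positive groin node found after primary excision. Such nodes are simply not expressly included.

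Nor is the direction of bias proven. An examiner who knows that a scan is suspicious may over-call palpability, which adds USM events and is conservative. The misfiling table models one direction only.

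**Conclusion.** The point holds as a gap in assignment. As written, no blinded body is charged with the palpable and skin-fixed call that turns a positive USM node into a primary event, and no text links the RAC's output to Sections 11.1 or 11.2.1.

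Given a prior that returns the printed stopping limits, one reclassified node at 6 events, or two at 7, changes safety not declared into safety declared. It would be tempting to say that one or two calls turn an unsafe result into a safe one. The figures do not support that: moving from 10/120 to 5/120 takes five, and at 6 to 9 the protocol allows for possible expansion. At a true 6% the chance of declaring safety rises from 27% to 37% or 48% with 10% or 20% misfiled. These sizes depend on the assumed prior and on illustrative misfiling rates, and they show sensitivity rather than expected bias.

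**What to change.** 1. Reconcile the endpoint wordings in the synopsis and Sections 5.5, 11.1 and 11.2.1 into one definition, including the time origin. Adjudicators cannot rule on components until this is done.
2. In 12.5, send the RAC every post-baseline groin node (found after the primary operation) that is histologically positive or palpable, and every death, in both randomised arms. Name scan-detected nodes explicitly.
3. Have the RAC rule on each endpoint component from all dated examination, operative and pathology records up to 12 months. Using only the examination at or before the triggering scan could discard true failures, because Sections 6.5.3 and 10.6.5.1 allow a woman to continue monitoring after a suspicious scan.
4. Mask scan-schedule details that reveal the arm as far as possible.
5. State in 11.1 and 11.2.1 that the RAC classification is the one analysed.

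The cost is modest, since the committee exists and already receives source documents: some additional case summaries. Two limits remain. Blinding will be imperfect for scan-detected nodes, because serial monitoring is not offered after groin dissection. And 12.5 says "The RAC review will be scheduled every 6 months from year 2 onwards for the duration of the study", so interim counts under 11.1 will rest on provisional classifications until the RAC has ruled.
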